## 7.2 Analysis of secondary endpoints

	e-CIG VS. IQOS Statistical Analysis Plan Version 2.0	Doc code: BIOSTAT.SAP.02
		Pag. 13 of 115

The secondary endpoints refer to the smoking reduction, the compliance to the study product and the acceptability of HnB or EC. The analyses to be performed on the smoking reduction and the adoption rate will be presented in sections 7.2.1 and 7.2.2 respectively. As for the latter, the endpoint will be analyzed through the product satisfaction, the risk perception, the effects on craving and nicotine withdrawal, the product preferences, the subjective and sensorial effects and presented in the sections from 7.2.3 to 7.2.8. In sections 7.3 and 7.4 the results of the analyses on the EQ-5D and the step test by visit will be presented.

### **7.2.1 Smoking reduction derived from the use of HnB and EC**

The smoking reduction derived from the use of HnB and EC, will be computed at each visit. The analysis will be presented considering both the definition of “Reducer” included in the study protocol and the so called “Russell Standard” (clinical) for outcome assessment in clinical trials of smoking cessation treatments.

As for the protocol definition, a subject will be classified as “Reducer” if at least a 50% reduction in the number of conventional cigarette/day at each visit will be observed. The results will be summarized as frequency table. The comparison between the two groups will be performed at each visit with the chi-square test. The results will be included in Table E.2a (Appendix 2).

As for the Russell Standard analysis, due to the fact that the study endpoint was a 12 weeks, a small deviation was adopted. In fact, the timepoint considered in the Russell Standard is 52 week. In our case, the 12 week and the 24 week (i.e. the Follow-up observation) will be considered for the analysis. The results will be included in Table E.2b (Appendix 2).

### **7.2.2 Adoption rate and adherence to product use**

The adoption rate and adherence to the product use will be analyzed on the basis of the subject's diary. The Sponsor will collect information relevant to the number of days of observation (i.e. last visit day – Informed Consent day) and the total of days of the device use. Those information will be collected in a derived dataset. The adherence to the product will be computed in term of rate according to the following formula:

$$Rate = \frac{Total\ days\ of\ device\ use}{Total\ days\ of\ study\ observation}$$

A subject is defined as “compliant” if the rate is at least a 90%. The comparison between the two groups will be performed with the chi-square test. The results will be included in Table E.3 (Appendix 2).

	e-CIG VS. IQOS Statistical Analysis Plan Version 2.0	Doc code: BIOSTAT.SAP.02
		Pag. 14 of 115

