### **Minimum Glossary**

**Efficacy:** the quit rate derived from the use of the product (HnB or EC)

**Adoption rate:** the daily product use (HnB or EC), measured independently from tobacco cigarette consumption

**Tolerability:** the incidence of adverse or serious adverse events derived from the use of the product (HnB or EC)

**Tobacco harm reduction:** reduction of selected biomarkers of exposure in spot urine and improvement in some biological parameters.

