#### *Secondary endpoints:*

- 2) To compare the smoking reduction derived from the use of HnB and EC, intended as a 50% reduction in the number of conventional cigarette/day at week 12, defined through self-reporting;
- 3) to compare the **adoption rate**, and adherence to product use [by collecting (empty) refill bottles and used heatsticks on a daily basis, verified by a study diary filled daily by the subject];
- 4) to compare the **acceptability** of HnB and of EC, through the assessment of product satisfaction, risk perception, effects on craving and nicotine withdrawal, product preferences, subjective and sensorial effects by:
  - a) Modified Cigarette Evaluation Questionnaire (mCEQ) adapted for EC and HnB users;
  - b) three of 8 items of "Smoking Cue Appeal" adapted for EC and HnBusers;
  - c) "Intent to use questionnaire" (ITUQ) – items 4-6;
  - d) PRI-P CC Perceived Health Risk scale (for classic cigarette)
  - e) PRI-P RRP Perceived Health Risk scale (for reduced risk products)
  - f) percentage of choice of a particular subtype of heatstick (HnB) or e-liquid.
- 5) to compare the **tolerability** of HnB and EC, in terms of: self-reported adverse and serious adverse events by study participants, vital signs (BP, HR and body weight) measurements.
- 6) to compare the **tobacco harm reduction** between HnB and EC, in terms of:
  - a) changes in Biomarkers of Biological Effects (BoBE) such as: eCO in the exhaled breath (i.e. eCO), step test values;
  - b) measurement of 14 selected Biomarkers of Exposure (BoE) in spot urine samples of study participants: 1 tobacco-specific nitrosamine, total NNAL (NNK); 8 volatile organic toxicants (derivates of mercapturic acid, MA): 2-hydroxyethylmercapturic acid (HEMA) also known as ethylene oxide, 2-hydroxy-3-butenylmercapturic acid and isomers (MHBMA) also known as 1,3-butadiene, 3-hydroxy-1-methyl propylmercapturic acid (HMPMA) also known as crotonaldehyde, 3-hydroxypropylmercapturic acid (3-HPMA) also known as acrolein, S-phenylmercapturic acid (S-PMA) also known as benzene, 2-carbamoylmercapturic acid (acrylamide mercapturic acid (AAMA) also known as acrylamide (AAMA and GAMA), 2-cyanoethylmercapturic acid (CEMA) also known as acrylonitrile, 2-hydroxypropylmercapturic acid (2-HPMA) also known as propylene oxide; 4 polycyclic aromatic hydrocarbons: naphthalene, fluorine, phenanthrene, pyrene (1-OHP); cotinine; creatinine.

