**Adoption rates and adherence to product use assessments:**

To compare the adoption rate, and adherence to product use in the two groups, we will collect (empty) e-liquid refill bottles and used heatsticks from V2 to V6, verified by a study diary filled daily by the subject, and their average consumption will be calculated on a daily basis. Final data source will be the study diary, in order to avoid underestimation of product usage due to forgetfulness in returning products, but we will evaluate also subjects’ reliability comparing the data reported in the diary and the returned product counting.

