**Follow-up Visit (V7):** Week 24 from V1 (with a tolerance of +/- 7 days): After 3 months from V6, a follow-up visit will be performed to assess the product usage and tolerability, medical/smoking/vaping/NGP behaviour, vital signs and weight/height measurement, step test, smoking abstinence/reduction assessment, quality of life perception assessment, acceptability assessment. It is remarked that the product free provision is stopped at V6.

Safety assessment (adverse and serious adverse events) and product reliability (eventual malfunctioning) will be monitored throughout the whole study and recorded in the eCFR.

**\*Remark:** At Baseline, during a period from 30 minutes to 2 hours, subjects will use and familiarize with their allocated product, as per randomization. In the same period, they will have the option to try and choose the preferred flavor of either e-liquid or heatstick, depending on the allocated arm. The choice must be maintained and cannot be changed for the 12-weeks study.

The subjects will be appropriately trained and counseled on the products, at baseline and during the whole study. Oral explanation, practical demonstration, brochures and direct help line with the investigators will be used for this objective. As specified in the exclusion criteria, the subjects will be alerted that, apart from using their allocated product and their own brand conventional cigarettes as they wish, they cannot use any other tobacco products during the 12-weeks study.

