XXXXXX	XXXXXX	XX/XXXX	XXXXXX	XXX XXXXXX XXXXXX XXXXXX	XXXXXXXXXXXXX XXXXXXXXXXXXX XXXXXXXXXXXXX XXXXXXXXXXXXX	XXXXX XXXXX XXXXX XXXXX	XXXXXXXXXXXXX XXXXXXXXXXXXX XXXXXXXXXXXXX XXXXXXXXXXXXX
XXXXXX	XXXXXX	XX/XXXX	XXXXXX	XXX XXXXXX XXXXXX XXXXXX	XXXXXXXXXXXXX XXXXXXXXXXXXX XXXXXXXXXXXXX XXXXXXXXXXXXX	XXXXX XXXXX XXXXX XXXXX	XXXXXXXXXXXXX XXXXXXXXXXXXX XXXXXXXXXXXXX XXXXXXXXXXXXX
XXXXXX	XXXXXX	XX/XXXX	XXXXXX	XXX XXXXXX XXXXXX XXXXXX	XXXXXXXXXXXXX XXXXXXXXXXXXX XXXXXXXXXXXXX XXXXXXXXXXXXX	XXXXX XXXXX XXXXX XXXXX	XXXXXXXXXXXXX XXXXXXXXXXXXX XXXXXXXXXXXXX XXXXXXXXXXXXX
XXXXXX	XXXXXX	XX/XXXX	XXXXXX	XXX XXXXXX XXXXXX XXXXXX	XXXXXXXXXXXXX XXXXXXXXXXXXX XXXXXXXXXXXXX XXXXXXXXXXXXX	XXXXX XXXXX XXXXX XXXXX	XXXXXXXXXXXXX XXXXXXXXXXXXX XXXXXXXXXXXXX XXXXXXXXXXXXX

<File: [..]\Work\_In\_Progress\[..]\Statistica\Programmi\xxxxx.sas>  
<Source: [..]\Work\_In\_Progress\[..]\Gestione Dati\Dati SAS\xxxxx.sas7bdat>      Generated on XXXXXXXX XX:XX

<Ordered by: Screening Number>  
<Stratified by: Group>  
<No. of sticks delivered - Preferred flavor@of heatstick / Quantity in mg/ml of e-liquid bottles - Preferred flavor@of e-liquid>

Sponsor: Center for Tobacco Research, Cessation and Prevention, [name]  
Protocol: Progetto e-cig vs IQOS

Listing D.10 Device supply and accountability < Group HnB / Group EC >

Screening Number	Random. Number	Age/Gender	Visit	<see footnote>
XXXXXX	XXXXXX	XX/XXXX	XXXXXXX	XXX
			XXXXXXX	XXX
			XXXXXXX	XXX
			XXXXXXX	XXX
			XXXXXXX	XXX
XXXXXX	XXXXXX	XX/XXXX	XXXXXXX	XXX
			XXXXXXX	XXX
			XXXXXXX	XXX
			XXXXXXX	XXX
			XXXXXXX	XXX
XXXXXX	XXXXXX	XX/XXXX	XXXXXXX	XXX
			XXXXXXX	XXX
			XXXXXXX	XXX
			XXXXXXX	XXX
			XXXXXXX	XXX

<File: [..]\Work\_In\_Progress\[..]\Statistica\Programmi\xxxxx.sas>

<Source: [..]\Work\_In\_Progress\[..]\Gestione Dati\Dati SAS\xxxxx.sas7bdat>      Generated on XXXXXXXXXX XX:XX

<Ordered by: Screening Number>

<Stratified by: Group>

< Average sticks consumed per day / No. of empty e-liquid refill bottles returned>

Sponsor: Center for Tobacco Research, Cessation and Prevention, [name]  
Protocol: Progetto e-cig vs IQOS

Listing D.11 Product use recording < Group HnB / Group EC >

Screening Number	Random. Number	Age/Gender	Q1	If yes, specify type and amount of daily use	Q2	If yes, average <sticks/e-liquid in ml consumed> per day
XXXXXX	XXXXXX	XX/XXXX	XXX	XXXXXXXXXXXXXXXXXXXXXXXXXXXX	XXX	XXXXXXXXXX

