XXXXXX	XXXXXX	XX/XXXX	XXX	XXXXXXXXXXXXXXXXXXXXXXXXXXXX	XXX	XXXXXXXXXX
XXXXXX	XXXXXX	XX/XXXX	XXX	XXXXXXXXXXXXXXXXXXXXXXXXXXXX	XXX	XXXXXXXXXX
XXXXXX	XXXXXX	XX/XXXX	XXX	XXXXXXXXXXXXXXXXXXXXXXXXXXXX	XXX	XXXXXXXXXX
XXXXXX	XXXXXX	XX/XXXX	XXX	XXXXXXXXXXXXXXXXXXXXXXXXXXXX	XXX	XXXXXXXXXX
XXXXXX	XXXXXX	XX/XXXX	XXX	XXXXXXXXXXXXXXXXXXXXXXXXXXXX	XXX	XXXXXXXXXX
XXXXXX	XXXXXX	XX/XXXX	XXX	XXXXXXXXXXXXXXXXXXXXXXXXXXXX	XXX	XXXXXXXXXX
XXXXXX	XXXXXX	XX/XXXX	XXX	XXXXXXXXXXXXXXXXXXXXXXXXXXXX	XXX	XXXXXXXXXX
XXXXXX	XXXXXX	XX/XXXX	XXX	XXXXXXXXXXXXXXXXXXXXXXXXXXXX	XXX	XXXXXXXXXX
XXXXXX	XXXXXX	XX/XXXX	XXX	XXXXXXXXXXXXXXXXXXXXXXXXXXXX	XXX	XXXXXXXXXX

<File: [..]\Work\_In\_Progress\[..]\Statistica\Programmi\xxxxx.sas>  
<Source: [..]\Work\_In\_Progress\[..]\Gestione Dati\Dati SAS\xxxxx.sas7bdat>      Generated on XXXXXXXX XX:XX

Q1: Did the subject use different RRP or other anti-smoking products during the last three months?  
Q2: If no, are you using the products delivered by this study?

<Ordered by: Screening Number>  
<Stratified by: Group>

	e-CIG VS. IQOS Statistical Analysis Plan Version 1.1	Doc code: BIOSTAT.SAP.02
		Pag. 81 of 115

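### The SAP reports a 90%-of-days adherence result as the adoption rate, and no SAP table summarises the daily amount of product used, which is how the protocol defines adoption

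*SAP*

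**What the plan says.** **Protocol.** The Minimum Glossary defines adoption rate as "the daily product use (HnB or EC), measured independently from tobacco cigarette consumption". Item 3 of the secondary endpoints names adoption rate and adherence as two things to compare, using returned refill bottles and "used heatsticks on a daily basis, verified by a study diary filled daily by the subject". The adoption and adherence assessment section says of e-liquid and heatsticks, "and their average consumption will be calculated on a daily basis". It also fixes the source: "Final data source will be the study diary, in order to avoid underestimation of product usage". Returned product serves as a check on the diary. The study design section adds that adoption is also recorded at 24 weeks.

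**SAP.** Section 7.2.2 is headed with both terms. The sponsor collects two items for it, days of observation and days of device use. Then: "The adherence to the product will be computed in term of rate according to the following formula". A subject with a rate of 90% or more is compliant, and the arms are compared by chi-square. Mock Table E.3 (week 12) has a single result row, Adoption Rate. Its footnote describes compliance as using 90% of the product, not 90% of days.

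**Data Review Meeting minute (SAP Appendix 5).** The adherence item says it confirms the SAP definition, but its denominator is days from V1 to V6. SAP 7.2.2 uses last visit day minus informed consent day.

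**Where amounts remain.** Daily amounts appear only in the subject listings of Appendix 3. The footnote to Listing D.10 gives "Average sticks consumed per day / No. of empty e-liquid refill bottles returned" for the two arms respectively. Mock Listing D.11 has average sticks or ml per day.

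**The concern.** Adoption and adherence answer different questions. Adoption, as the protocol defines it, is how much of the product a participant uses per day. Adherence is on what share of days the product is used at all. The SAP computes only the second and labels it as the first. A reader of the statistical report would see an Adoption Rate with a confidence interval and p-value and take it for the protocol's endpoint, when it carries no information on amount.

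A separate problem is that the adherence figure depends on which of three stated rules the programmer follows, so the same diary can give different classifications.

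**Working it through.** **Step 1. The plan's own figure.** The Data Review Meeting minute gives a worked example, 45 days of use over 90 days from V1 to V6. 45/90 = 0.50, as stated. The rule is a pure day count.

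**Step 2. Endpoint against analysis.**

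| Protocol construct | Protocol measure | SAP analysis |
|---|---|---|
| Adoption rate | Average sticks or e-liquid per day, from the diary | None; E.3 carries only the name |
| Adherence | Not given a separate formula | Days used / days observed, at least 0.90, chi-square |

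The table list in SAP Appendix 1 and the mock tables in Appendix 2 contain no table of sticks/day or ml/day at any visit. Table E.3 stops at week 12, so adoption at week 24 has no table either.

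**Step 3. Can the two measures disagree?** Assumptions: 84 days from V1 to V6 (12 weeks, from the visit schedule), and daily amounts of 1 and 20 sticks, which the documents do not give.

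- Subject A, 1 stick on every day: rate 84/84 = 1.00, compliant. Total 84 sticks; 84/84 = 1.0 stick/day.
- Subject B, 20 sticks on 75 days, none on 9: rate 75/84 = 0.893, below 0.90, not compliant. Total 20 × 75 = 1,500 sticks; 1,500/84 = 17.9 sticks/day.

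Range for the assumed amount: with k sticks on each of 75 days, the average is 75k/84 = 0.893k. This gives 1.8 sticks/day at k = 2, 8.9 at k = 10 and 17.9 at k = 20. The average exceeds A's whenever k is above 84/75 = 1.12. The reversal therefore does not depend on choosing 20.

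**Step 4. How many missed days make a daily user fail?** Days needed = 0.90 × denominator, rounded up. Inputs: V6 at 12 weeks ± 7 days, V1 within 7 days of V0, V7 at 24 weeks. Consent is at V0 in the protocol's visit description and the SAP flow chart, but at V1 in the protocol's schedule table. The rows with consent 3 or 7 days before V1 are assumed cases within that window.

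| Denominator | Days | Highest possible rate | Days needed | Missed days that fail |
|---|---|---|---|---|
| V1 to V6, nominal | 84 | 84/84 = 1.00 | 76 | 9 |
| V1 to V6, 7 days early | 77 | 77/77 = 1.00 | 70 | 8 |
| V1 to V6, 7 days late | 91 | 91/91 = 1.00 | 82 | 10 |
| Consent 3 days before V1, to V6 | 87 | 84/87 = 0.966 | 79 | 6 |
| Consent 7 days before V1, to V6 | 91 | 84/91 = 0.923 | 82 | 3 |
| V1 to V7, use counted to V6 only | 168 | 84/168 = 0.50 | 152 | nobody passes |
| Consent 7 days before V1, to V7, use counted to V6 only | 175 | 84/175 = 0.48 | 158 | nobody passes |

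A subject who misses 3 days scores 81/84 = 0.964 (compliant) under the minute's rule and 81/91 = 0.890 (not compliant) under SAP 7.2.2 with consent 7 days before V1. The last two rows apply only if last visit is read as V7. The week-12 title of E.3 points to V6, but 7.2.2 does not say so.

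**The case against.** The strongest defence is that a days-used ratio is a legitimate adherence measure, that adherence is half of the protocol's objective, and that the study team confirmed the rule. The ratio also has no unit, so the arms can be compared, whereas sticks and millilitres cannot. All of that stands. It justifies keeping the analysis, but not calling it adoption or leaving adoption without a summary.

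SAP section 5 promises descriptive statistics by group for all data. That general sentence does not secure the endpoint, because no table is specified and the 7.2.2 derived dataset is described as holding day counts only.

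The E.3 footnote could be read as an amount. Even so, a share of the product used is not average daily consumption, and it contradicts 7.2.2.

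The SAP says compliant and never adopter; the link to adoption is the section heading and the E.3 row label. Nor do the documents show how often a reversal like that in Step 3 would occur.

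Three stronger readings are tempting and are not supported:

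- A reader might infer that the rule fails because it cannot tell full switchers from people who also smoke. The protocol measures adoption independently of cigarettes and lets participants carry on, "apart from using their allocated product and their own brand conventional cigarettes as they wish". Switching is covered by the quit and reduction endpoints, and sticks/day would not detect it either.
- A reader might infer that anyone using another product has no week-24 value, because the Listing D.11 footnote says "Q2: If no, are you using the products delivered by this study". This is one footnote in a mock listing. The eCRF is not in the documents, so an enforced skip is not established. That D.11 is the week-24 form is itself an inference, from its three-month recall and the product-history item at V7.
- A reader might infer from the unlike units in Listing D.10, with no bottle volume stated, that e-liquid use cannot be recovered. D.10 is an accountability listing, and the protocol makes the diary the final source.

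**Conclusion.** The point holds as a mismatch between a named secondary endpoint and its planned analysis. Followed as written, the SAP reports adherence under the name of adoption and leaves the protocol's daily amount unsummarised at week 12 and week 24. The Step 3 figures illustrate that the two measures can order users differently; they rest on the assumed 84 days and assumed stick counts and do not estimate frequency.

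The compliance rule also needs reconciling. A daily user first fails at 8 to 10 missed days under the minute's V1-to-V6 rule. Under SAP 7.2.2 the threshold is 6 or 3 missed days if consent comes 3 or 7 days before V1 and the last visit is V6. The E.3 footnote adds a third, amount-based wording.

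This should be corrected. It does not touch the primary non-inferiority test or the 104 per group.

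**What to change.** 1. Relabel the E.3 row, and its title in Appendix 1, as adherence. Keep the 90%-of-days rule and the chi-square test there.
2. State one denominator and one definition, and make SAP 7.2.2, the Data Review Meeting minute and the E.3 footnote agree. V1 to V6 is the period of free supply, and under it a daily user can reach 1.00.
3. Add one descriptive adoption table to 7.2.2: average sticks/day (HnB) and ml/day (EC) from the diary, by arm and visit interval from V1 to V6.
4. In the same table, give week 24 from the values already recorded in Listing D.11, with the number missing by arm.

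The cost is SAP wording and one table. Sticks and millilitres share no unit, so amounts are described by arm and not tested between arms. E-liquid ml/day may have to be extracted from the diaries, since 7.2.2 describes only day counts for its derived dataset. No new data collection or eCRF change is asked for: by SAP 2.0 the 177 subjects of the Per-Protocol V7 population had been counted and the database had already been frozen once.

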### 7.2.3 Modified Cigarette Evaluation Questionnaire

The modified Cigarette Evaluation Questionnaire (mCEQ) will be presented as descriptive summary table by visit. Acceptability of HnB and of EC will be analyzed through the assessment of several questionnaires. The analyses will be presented in three multi-item domains (i.e. Smoking Satisfaction, Psychological Reward and Avversion) and two single-item domains (i.e. Cravin Reduction and Enjoyment of Respiratory Tract Sensation). Changes from the Baseline Visit to all the subsequent study visits will be also generated. The results will be included in Table E.4a1 (Appendix 2).

The t-test will be carried out on the differences at final visit to baseline. In case the normality assumption is not verified, the corresponding non parametric test will be adopted. The results will be included in Table E.4a2 (Appendix 2). These data will also be listed (Appendix 3: Listing E.2).

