**Acceptability assessment:**

Product satisfaction, effects on craving and nicotine withdrawal, product preferences, risk perception, subjective and sensorial effects to compare the acceptability of HnB and of EC, will be evaluated at wk 4, wk 8, wk 12 (+ follow-up at wk 24), by using:

- a) Modified Cigarette Evaluation Questionnaire (mCEQ) adapted for EC and HnB users;
- b) three of 8 items of “Smoking Cue Appeal” adapted for EC and HnBusers;
- c) “Intent to use questionnaire” (ITUQ) – items 4-6;
- d) PRI-P CC Perceived Health Risk scale (for classic cigarette)
- e) PRI-P RRP Perceived Health Risk scale (for reduced risk products)
- f) percentage of choice of a particular subtype of heatstick (HnB) or e-liquid.

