**Tobacco Harm Reduction assessment:**

a) we will record changes in Biomarkers of Biological Effects (BoBE) such as: eCO in the exhaled breath (i.e. eCO) will be assessed at each study visit (+ follow-up at wk 24); step test values at baseline, wk 4, wk 12 (+ follow-up at wk 24).

b) measurement of 14 selected Biomarkers of Exposure (BoE) in spot urine samples of study participants, at baseline (V1) and wk 4 (V4):

tobacco-specific nitrosamine, total NNAL (NNK); 8 volatile organic toxicants (derivates of mercapturic acid, MA): 2-hydroxyethylmercapturic acid (HEMA) also known as ethylene oxide, 2-hydroxy-3-butenylmercapturic acid and isomers (MHBMA) also known as 1,3-butadiene, 3-hydroxy-1-methyl propylmercapturic acid (HMPMA) also known as crotonaldehyde, 3-hydroxypropylmercapturic acid (3-HPMA) also known as acrolein, S-phenylmercapturic acid (S-PMA) also known as benzene, 2-carbamoylethylmercapturic acid (acrylamide mercapturic acid (AAMA) also known as acrylamide (AAMA and GAMA), 2-cyanoethylmercapturic acid (CEMA) also known as acrylonitrile, 2-hydroxypropylmercapturic acid (2-HPMA) also known as propylene oxide; 4 polycyclic aromatic hydrocarbons: naphthalene, fluorine, phenanthrene, pyrene (1-OHP); cotinine; creatinine.

**Lab analysis:** urine samples will be collected at baseline and wk 4, and sent to an external laboratory to search for any modifications in the above mentioned Biomarkers of Exposure (BoE); the lab selected is ABF GmbH: SOPs for urine collection and lab procedures are available and briefly described in the quotation attached.

c) Self-perception of “Tobacco Harm Reduction process” will be assessed by changes in quality of life score at baseline, wk 4, wk 8, wk 12 (+ follow-up at wk 24). The quality of life will be assessed by a validated visual analogic scale specifically designed to measure this topic and named “EQ-5D”;

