**Visit schedule description:**

**V0:** Screening visit for eligibility criteria. Recording of the medical history and smoking behavior of the participant. Selected participants will sign an Informed Consent. Selected participants will be instructed on how to collect and store their first morning urine (containers for urine collection will be delivered to them during the screening) before bringing it to the hospital on the day established for Baseline/Visit 1. (SOPs are available).

**Visit 1 (V1)** (to be programmed within 1 week from V0): Eligibility criteria confirmation, All Baseline assessments, Self-reported daily conventional cigarette consumption recording (baseline measurement), Randomisation, HnB or EC free supply for 1 week and familiarization period to choose the preferred flavor\* (30 min to 2h, as specified below), training on product use, spot urine samples collection and storage.

**Visit 2 (V2):** Week 1 from V1 (with a tolerance of +/- 3 days): vital signs measurement, smoking abstinence/reduction assessment (self-reporting + eCO measurement), adoption rates assessment, HnB or EC free supply for 1 week.

**Visit 3 (V3):** Week 2 from V1 (with a tolerance of +/- 3 days): vital signs measurement, smoking abstinence/reduction assessment, adoption rates assessment, HnB or EC free supply for 2 weeks, repeat instructions for first morning urine collection and storage at V4 and delivery of containers.

**Visit 4 (V4):** Week 4 from V1 (with a tolerance of +/- 3 days): Second hand over of spot urine samples, vital signs measurement, smoking abstinence/reduction assessment, adoption rates assessment, quality of life perception assessment, HnB or EC free supply for 4 weeks, step test, acceptability assessment.

**Visit 5 (V5):** Week 8 from V1 (with a tolerance of +/- 7 days): vital signs measurement, smoking abstinence/reduction assessment, adoption rates assessment, quality of life perception assessment, HnB or EC free supply for 4 weeks, acceptability assessment.

**Visit 6 (V6):** Week 12 from V1 (with a tolerance of +/- 7 days): vital signs and weight/height measurement, smoking abstinence/reduction assessment, adoption rates assessment, quality of life perception assessment, acceptability assessment. End of product free provision.

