### 2.5 Study Plan

This study has been structured considering a Screening visit (V0), a Baseline visit (V1), a week 1 visit, a week 2 visit, a week 4 visit, a week 8 visit, a week 12 visit. A prospective evaluation of efficacy, adoption rates, acceptability and tolerability will be also recorded at 24-weeks, through a follow-up visit (V7).

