### **6.7 Fagestorm test for nicotine dependence**

	e-CIG VS. IQOS Statistical Analysis Plan Version 2.0	Doc code: BIOSTAT.SAP.02
		Pag. 12 of 115

The results of the Fagestorm test for nicotine dependence (FTCD) will be presented as frequencies and percentages for the single questions and total scores derived from the questionnaire through n, missing, mean, standard deviation and 25th, 50th, 75th percentiles (Appendix 2: Table D.7). These data will also be listed (Appendix 3: Listing D.11).

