## **APPENDIX 4 Flow Chart**

	V0 screening	V1 baseline	V2	V3	V4	V5	V6	V7 follow-up
Assessment		≤ 7 days after V0	1 week after visit 1 +/-3 days	2 weeks after visit 1 +/-3 days	4 weeks after visit 1 +/-3 days	8 weeks after visit 1 +/-7 days	12 weeks after visit 1 +/-7 days	24 weeks after visit 1 +/-7 days
Medical/smoking/vaping/new generation product use history	X							X
Instructions for urine collection and storage; delivery of containers	X			X				
Eligibility criteria verification and confirmation	X							
Informed consent	X							
Vital Signs (BP, HR)		X	X	X	X	X	X	X
Weight and Height		X					X	X
Urine sample pick up		X			X			
Randomization		X						
Training for the allocated device (from 30min to 2 hours)		X						
Device delivery (included 1 week supply heatsticks for iQOS or eliquid for JustFog)		X						
Providing 1 week supply of heatsticks for iQOS or eliquid for JustFog			X					
Providing 2 weeks supply of heatsticks for iQOS or eliquid for JustFog				X				

Providing 4 weeks supply of heatsticks for iQOS or eliquid for JustFog					X	X		
Smoking consumption/abstinence/reduction recording through subject selfreporting		X	X	X	X	X	X	X
Device and supply accountability (collection of empty e-liquid refill bottles and used heathsticks; eventual substitution of malfunctioning devices)			X	X	X	X	X	X
mCEQ					X	X	X	X
Smoking Cue Appeal (8 items)					X	X	X	X
ITUQ – items 4-6					X	X	X	X
Risk perception (PRI-P CC e PRIP RRP)					X	X	X	X
EQ-5D		X			X	X	X	X
eCO		X	X	X	X	X	X	X
Step test		X			X		X	X
Safety and product reliability onitoring reporting		X	X	X	X	X	X	X

e-CIG VS. IQOS  
Statistical Analysis Plan  
Version 1.1

Doc code:  
BIOSTAT.SAP.02

Pag. 95 of 115

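### Five acceptability questionnaires are to be tested on change from baseline, but no baseline score is scheduled for any of them

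*SAP*

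**What the plan says.** SAP 7.2.3 (mCEQ) states: "The t-test will be carried out on the differences at final visit to baseline". Sections 7.2.4 to 7.2.7 repeat the rule for Smoking Cue Appeal, ITUQ, PRI-P CC and PRI-P RRP, each with a non-parametric fallback. The matching shells, Tables E.4a2 to E.4e2, show one mean per group and one p-value per row, so the intended test is between groups. Section 7.2.3 also asks for descriptive mCEQ changes from baseline at every later visit, and Table E.4a1 has change-from-Visit-1 columns for them.

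SAP 2.5 identifies the baseline visit: "This study has been structured considering a Screening visit (V0), a Baseline visit (V1").

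The protocol's acceptability paragraph says these scales "will be evaluated at wk 4, wk 8, wk 12 (+ follow-up at wk 24), by using" the listed instruments. In its visit descriptions, acceptability first appears at Visit 4: "HnB or EC free supply for 4 weeks, step test, acceptability assessment". The protocol visit schedule and the SAP Appendix 4 flow chart mark the rows for these scales (for example "Smoking Cue Appeal (8 items")) under Visits 4, 5, 6 and 7 only.

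For EQ-5D the protocol does name a baseline. That outcome "will be assessed by changes in quality of life score at baseline, wk 4, wk 8, wk 12 (+ follow-up at wk 24").

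**The concern.** A change score needs two values, and for these five scales the plan schedules only the later one. Comparing acceptability is a stated secondary objective in both documents, and one of the three planned publications covers satisfaction, craving, preferences and risk perception. If the specified test has no input, some other contrast must take its place, and the SAP names none. The data review minute (SAP Appendix 5, 2.5) requested no change to the SAP. SAP section 1 requires only that deviations be explained in the report. Without a correction, the contrast and the visit would be chosen during analysis, in an open-label trial whose data are already collected. The choice of visit could matter, because free product ends at Visit 6: "It is remarked that the product free provision is stopped at V6".

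**Working it through.** The plan gives no figure of its own on this point. The check sets the visits each test needs against the visits scheduled, then counts the affected p-values and sizes the replacement.

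**1. Scheduled visits** (protocol schedule, SAP Appendix 4, by-visit shells)

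| Scale | Visit 1 | Visits 4, 5, 6, 7 | First row of by-visit shell |
|---|---|---|---|
| mCEQ | no | yes | Visit 4 (E.4a1) |
| Smoking Cue Appeal | no | yes | Visit 4 (E.4b1) |
| ITUQ items 4-6 | no | yes | Visit 4 (E.4c1) |
| PRI-P CC | no | yes | Visit 4 (E.4d1) |
| PRI-P RRP | no | yes | Visit 4 (E.4e1) |
| EQ-5D (for contrast) | yes | yes | Visit 1 (E.6) |

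Baseline scores are scheduled for 0 of the 5 scales. Post-baseline assessments number 4 for each.

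**2. Could a baseline come from elsewhere?**
- The Visit 1 description has a general entry for baseline assessments, but it names no questionnaire, and the schedule rows for these scales are blank at Visit 1.
- Some collected items are missing from the schedule, but they surface in the SAP's baseline material. One is the dependence test in SAP 6.7 ("The results of the Fagestorm test for nicotine dependence (FTCD) will be presented as frequencies and percentages"); another is screening eCO in Table D.2b. None of the five scales appears in SAP section 6.
- LOCF (SAP 5.1) carries values forward, so it cannot create a baseline.

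**3. P-values affected, per analysis population** (items plus total, from shells E.4a2 to E.4e2)
- mCEQ 5 + 1 = 6; Smoking Cue Appeal 8 + 1 = 9; ITUQ 3 + 1 = 4; PRI-P CC 18 + 1 = 19; PRI-P RRP 18 + 1 = 19.
- Sum: 6 + 9 + 4 + 19 + 19 = 57.
- The objectives and the protocol's acceptability paragraph specify three of the eight Smoking Cue Appeal items. On that basis the row count is 3 + 1 = 4 and the sum is 6 + 4 + 4 + 19 + 19 = 52.

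**4. Precision of a Visit 6 comparison**

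Half-width of the 95% CI in SD units = t(0.975, n1 + n2 − 2) × √(1/n1 + 1/n2), with equal SDs. SAP 9.7 gives the totals 193 (Per-Protocol) and 217 (ITT); the arm splits are assumptions.
- Per-Protocol, 96/97: 0.284. Per-Protocol, 83/110 (the most uneven split if 110 per arm were randomised as planned): 0.287.
- ITT, 108/109 and 107/110: both 0.268.

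These are best cases. The ITT population needs only one post-baseline observation, and the data review minute keeps subjects who left after Visit 2 in it. Anyone who left before Visit 4 has no score to carry forward. There are 217 − 193 = 24 subjects in ITT beyond the Per-Protocol count, and the documents do not say how many of them left that early. The PRI-P shells also exclude don't-know answers (score 6). That lowers n by an unknown amount in 19 + 19 = 38 of the 57 rows.

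**The case against.** The strongest defence is that little depends on these tests. The SAP calls its analysis descriptive and speaks only of possible inferential analyses. The protocol's statistics section sets no specific acceptability test; its general sentence on between-group tests sits under safety and names no scale or visit. The same change-from-baseline sentence is valid for EQ-5D in SAP 7.4, which suggests carried-over wording. All of this stands, and it limits the consequence. It does not make the prescribed tests computable.

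It can also be said that any replacement is now chosen after data collection. That is correct: the data review had already counted 177 subjects in the Per-Protocol V7 population. Recording the contrast before the second freeze prevents a choice during analysis, but it does not make the contrast prespecified.

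A reader might infer more than the documents support:
- *That acceptability can no longer be compared at all.* By-visit summaries are planned for both groups, flavour choice has its own table, and scores at a single visit can be compared.
- *That no baseline scores were ever collected.* The documents show only that none was scheduled. If unscheduled scores exist in the eCRF, the schedules and shells are wrong and still need correcting.
- *That all 217 ITT subjects would contribute to the replacement.* Those without any score from Visit 4 onward cannot.

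**Conclusion.** The point holds as a contradiction within the plan. The change-from-baseline tests for all five scales, and the mCEQ change columns, have no scheduled input. That affects 57 p-values per population on the shells, or 52 with three Smoking Cue Appeal items. These are the only between-group tests the SAP specifies for the acceptability questionnaires, so the matter should be fixed. The primary endpoint, the sample size and the descriptive tables do not depend on it.

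A second gap goes with it: sections 7.2.3 to 7.2.7 do not say whether the final visit is Visit 6 or Visit 7. Shell E.4a1 fills its change columns only on the Visit 7 row, although the text of 7.2.3 asks for changes at all later visits.

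A replacement is feasible. Its half-width is at best about 0.28 to 0.29 SD in the Per-Protocol population, assuming the arm splits shown and a score for every subject, and is wider for PRI-P rows. The 0.27 SD figure for ITT is a lower bound.

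**What to change.** In SAP 7.2.3 to 7.2.7, replace the change-from-baseline test with a between-group comparison of the observed score, reporting the mean difference and 95% CI or the non-parametric equivalent.

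- Name the visit. Use Visit 6 (week 12, the end of the treatment period and of free product) as the main comparison and Visit 7 as supportive.
- Do not relabel Visit 4 as a baseline, because it is post-randomisation and follows four weeks of product supply.
- Delete the change columns of Table E.4a1 and the matching sentence in 7.2.3. Retitle Tables E.4a2 to E.4e2 and their five Appendix 1 entries.
- SAP 7.4 sends the EQ-5D change test, which is valid, to Table E.4a2. Give that test its own table.
- State whether three or eight Smoking Cue Appeal items are analysed.
- Report n for each row, so that the loss from early leavers and don't-know answers is visible.
- Record the change before the second database freeze (data review minute, 2.8) and state that it was made after data collection.

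The cost is edits to six SAP subsections (7.2.3 to 7.2.7 and 7.4), six shells (E.4a1 and E.4a2 to E.4e2) and five Appendix 1 titles, plus a table and Appendix 1 entry for the EQ-5D test. No new data are needed.
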